7.4 Reporting Procedures

An internal log of all AE, SAE, UP and PD events that come to the attention of the staff will be maintained.

Unanticipated Problems will be reported to the IRB using the Reportable Events Form within 5 business days of the identification of the event by the research staff.

RAs will maintain a daily attendance log throughout the intervention. If a participant is not in attendance at any of the sessions it will be recorded and they will attempt to get in touch with the participant. If it comes to their attention that an adverse even has taken place they will document this on the attendance log and fill out an AE form and/or SAE form if necessary. All adverse events will be compiled and reported on an ongoing basis and in summary form at the conclusion of the study to the IRB, the DSMB medical officer ([name]) and the NIA program officer ([name]. [name]). Unanticipated (non-serious) adverse events will be reported within 30 days via submission of an Adverse Event Report. Serious adverse events will be reported within 24 hours by phone, email or fax. A completed Adverse Event Report will be submitted within 10 days of initial notification. All deaths will be reported within 24 hours.

If PIs become aware of issues that threaten the integrity of the trial or participant safety, they will alert the NIA representative to the DSMB who will consult with the DSMB Chair as to whether a special meeting or conference call of the DSMB should be held.

7.5 Follow-up for Adverse Events

AEs will be followed until resolved or considered stable.

7.6 Safety Monitoring

Prior to beginning data collection, [name] and the DSMB Chair will reconfirm that our site has appropriate safety measures in place. The DSMB will meet with the entire research team to review the study protocols. Particular attention will be paid to outcome definition, study design, procedures for recording and reporting adverse events, and informed consent procedures and documentation.

At the initial meeting, the DSMB may recommend modifications or clarification of the protocol, and it will formulate its operating procedures (e.g., meeting schedule, reports due dates for the study statistician, unblinding policy, and what interim data may be released to the investigators). At the initial meeting the plans for interim monitoring for efficacy and futility will be presented to the DSMB as an aid for monitoring the trial.

We will train competent staff to conduct the interventions and assessments, ensure they understand the nature of the interventions, and understand adverse event reporting requirements. Trained clinical assistants, who will monitor the subject for any adverse events, will perform all assessments. We do not expect any serious adverse events during these non-invasive interventions. The clinical assistant will stop the testing procedures if subjects feel stressed or get embarrassed by their performance, and relay the information immediately to [name] or [name]. At least one investigator will be present onsite during all testing and intervention sessions. In addition Drs. [name] and [name] will be available by cellular telephone at all times to address any safety concerns or clinical issues.

Please see the Safety Monitoring Guidelines for further details (DSMP).

8 INTERVENTION DISCONTINUATION

Early study termination will occur in the event of any unanticipated serious adverse event determined to be possibly, probably or definitely related to study procedures, failure to recruit at least 50% of the projected number of subjects within 4 months, or failure to retain at least 75% of study subjects to the conclusion of the protocol.

Subjects may withdraw voluntarily from participation in the study at any time and for any reason. If the participant is acutely ill, is in the hospital, or has a temporary condition that interferes with walking (e.g. ankle sprain), we will attempt to complete the assessment at another time. We will follow-up with participants who dropped out of the study to determine both their mobility status and reasons for withdrawal. We will use intention to treat (ITT) analysis, which includes all randomized participants in the groups assigned, regardless of adherence with entry criteria, whether motor imagery was received, and subsequent withdrawal or deviation from the protocol. ITT analysis is pragmatic because it admits noncompliance and protocol deviations, and gives an unbiased estimate of the intervention effect. Handling missing data is a major issue in ITT, and is dealt with by imputation or sensitivity analysis. Our statistician, [name], is very experienced in these methods.

A rich set of telephone-based information will be collected even for those subjects who may drop out. We will utilize this auxiliary information to assess the MAR assumption and combine it into the main model through joint modeling and multiple imputation approaches.

The research team will adjudicate events such as mobility disability in subjects who drop out based on medical interviews, contact interviews, and home assessments as required. For each study assessment, we will allow a 4-week window for completion.

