1 STUDY OBJECTIVES

1.1 Primary Objective

Compared to a visual imagery intervention group, the participants who are enrolled in the motor imagery intervention group will demonstrate significant improvements in gait speed (cm/s) during actual Walking and Walking While Talking using an instrumented walkway (GAITRite® electronic walkway system).

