3 STUDY DESIGN

Design: We propose a single-blind study of cognitively-healthy older adults randomized to a phone-based motor imagery or visual imagery (active control) intervention for 12 weeks (36 sessions)

Outcomes: The primary outcome is post-intervention change in gait speed during actual walking and walking while talking.

Secondary and tertiary outcomes include improvements in cognitive performance during Talking and Walking While Talking, changes in blood-oxygen-level dependent signal during Walking and Walking While Talking, improvement in executive function, and other mobility-related cognitive processes (speed of processing, memory and spatial navigation), and improved gait variability and other quantitative gait parameters during walking and walking while talking (see Clinicaltrials.gov-NCT02762604 for a comprehensive list).

Study population: 48 Bronx and Westchester county residents between 65 and 85 years old will be randomized into a phone-based motor imagery or visual imagery (control) intervention for 12 weeks (36 sessions)

Study location: Pre and post-intervention visits will be held at the Albert Einstein College of Medicine.

Approximate duration of enrollment period and follow-up: Potential recruits who meet eligibility criteria on the telephone are invited to baseline assessment and then randomized to motor imagery or visual imagery intervention. Baseline study assessments are limited to 180 minutes over 1 day to avoid fatigue. Telephone assessments are 15 minutes. Post-intervention assessments will be conducted within 4 weeks of the completion of the intervention.

We plan to enroll and randomize 48 participants over 36 months (1-2 per month). If necessary, we will ask for a no cost extension to allow for additional time to process and analyze the data, write manuscripts, and possibly apply for a follow-up grant.

Randomization and Blinding: We will include a number of methods to reduce bias.

- Selection bias will be reduced by concealing treatment allocation until the participant is entered into trial.
- Primary outcome is an objective endpoint (gait speed) and not subjective mobility complaints.
- Motor imagery and visual imagery interventions will be administered individually, and at non-overlapping times.
- Participants and study staff will be instructed not to disclose group assignment or details of interventions.

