5.4 Adherence Assessment

Sustaining adherence represents a major challenge in any RCT involving older adults. The phone-based delivery of the RCT improves likelihood of adherence. We have also incorporated multiple methods to promote adherence and reduce possibility of missing data.

- A permanent staff contact will be provided for each participant in the motor imagery and visual imagery intervention groups.
- Transportation and snacks will be provided on pre and post intervention assessment days.
- All participants will be compensated for attending in-house or telephone sessions (\$50 for the baseline visit, \$25 for the phone-based intervention, and \$50 for the post-intervention visit, for a total of \$125 for the study).

We propose to over-enroll by 20% to account for any attrition. Methods to account for non-compliance and missing data:

- Protocol violations. Subjects who miss 6 sessions due to any reason will be excluded from main analyses. We will explore dose response by adjusting number of sessions attended as a

covariate.

- We will identify 2 contact persons who do not live with the participant for when participant cannot be reached.
- Flexible scheduling with makeup sessions on alternate days.
- For each in-house study visit, we will allow a four-week window for completion.
- If the participant is acutely ill, is in the hospital, or has a temporary condition that interferes with walking (e.g. ankle sprain), we will attempt to complete the assessment at another time.
- Outcome adjudication. The research team will adjudicate events such as mobility disability in subjects who drop out based on medical interviews, contact interviews, and home assessments as required.

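### The follow-up of dropouts does not provide for measuring gait speed, so the promised ITT analysis would impute some primary outcomes that could have been measured

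*Combined protocol and SAP*

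**What the plan says.** Section 3 defines the endpoint: "The primary outcome is post-intervention change in gait speed during actual walking and walking while talking." Section 1.1 gives the unit as cm/s and names a walkway system as the instrument. The schedule in Section 6.1 lists that system as a study-visit measure only. Section 6.2.3 places the post visit within 4 weeks after the intervention has been completed.

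For people who leave, the plan provides the following:

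- Sections 6.2.4 and 8: "We will follow-up with participants who dropped out of the study to determine both their mobility status and reasons for withdrawal."
- Sections 5.4, 6.2.4 and 8: "The research team will adjudicate events such as mobility disability in subjects who drop out", using interviews and, where needed, home assessments.
- Sections 6.2.4 and 8: "A rich set of telephone-based information will be collected even for those subjects who may drop out." The plan will use these data to examine the missing-at-random assumption and will "combine it into the main model through joint modeling and multiple imputation approaches."
- Sections 5.4, 6.2.4 and 8: an assessment is tried again later if the participant is acutely ill, in hospital or has a temporary walking problem.

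On the analysis set, Section 8 states: "We will use intention to treat (ITT) analysis, which includes all randomized participants in the groups assigned." Section 5.4 instead removes from the main analyses anyone who misses 6 sessions.

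**The concern.** An ITT comparison needs the post-intervention gait speed of every randomised participant, or a credible substitute for it. The walking test is short and does not depend on having finished the calls. A participant who tires of the calls but stays willing and able to walk can still supply the outcome.

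The plan does not describe that participant. Section 8 is headed as intervention discontinuation, but its text deals with early termination of the study and withdrawal from it. Stopping the calls is not distinguished from refusing further assessment. Because the post visit is timed from completion of the intervention, someone who stops early has no stated date for it. The provision to retry an assessment covers temporary inability, not loss of interest.

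People who give up on imagery calls may respond differently from those who finish. Section 6.2.4 itself says that prevention is the best answer to missing data and that informative loss biases the results unless adjusted for. The claim in Sections 6.2.4 and 8 that ITT is unbiased depends on the outcomes being observed, or on the imputation model being right.

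**Working it through.** **1. What the analysis needs against what is collected.**

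| Item | Obtained from dropouts? | Yields gait speed on the walkway? |
|---|---|---|
| Mobility status, reasons for leaving | Yes (6.2.4, 8) | No |
| Adjudicated events such as mobility disability | Yes (5.4, 6.2.4, 8) | No |
| Telephone data | Yes (6.2.4, 8) | No; auxiliary for imputation |
| Walking and walking-while-talking speed | Not provided for | – |

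Sections 1, 3 and 9 do not list mobility status or mobility disability as outcomes. Section 9.1.2 mentions disability scales only as additional variables or potential covariates. Section 9.4.1 names a repeated-measures analysis and does not mention imputation, and no section specifies an imputation model.

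**2. How many are affected.** Inputs from Section 9.2: 58 enrolled, 48 completing, 18% attrition.

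- 58 − 48 = 10, and 10/58 = 17%. By the stated rate, 0.18 × 58 = 10.4, or about 5 per arm (0.18 × 29 = 5.2).
- The Précis and Section 3 give 48 as the number enrolled. On that reading, 0.18 × 48 = 8.6.
- The retention rule in Section 8 tolerates a 25% loss: 0.25 × 58 = 14.5, so up to 14.

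The plan does not split attrition by cause, so the share that could be measured is unknown.

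**3. What missing outcomes can do: an illustration.** Let p be the fraction missing, equal in both arms. Let Δc be the arm difference among completers and Δd that among dropouts. Then:

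- ITT effect = (1 − p)Δc + pΔd
- completer estimate − ITT effect = p(Δc − Δd)

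If motor imagery dropouts gain nothing over control dropouts (Δd = 0) and p = 0.18, the ITT effect is 0.82Δc. The completer estimate then overstates it by a factor of 1/0.82 = 1.22, that is 22%.

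Suppose half of those dropouts were measured (an assumption), and those still missing were like them. The observed estimate becomes 0.82Δc/0.91 = 0.90Δc, and the overstatement falls to 0.90/0.82 = 1.10, or 10%.

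**4. Whether measuring dropouts costs power.** The plan's n = 34 is reproduced first. The test is a 1-df group-by-time contrast with λ = f²·N·m/(1 − ρ), f = 0.25, m = 2, α = 0.05 and ρ = 0.5. The plan does not state ρ, so 0.5 is assumed. At N = 34, λ = 0.0625 × 34 × 2/0.5 = 8.5 and power is 0.807, which agrees with the plan. The required N depends on ρ: 66 at 0, 46 at 0.3 and 22 at 0.7.

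With ρ = 0.5:

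- 48 completers: power 0.92.
- All 58 measured, full effect in all: power 0.96.
- All 58 measured, no effect in the 10 dropouts: f = 0.25 × 48/58 = 0.207, power 0.87.

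Under the plan's own inputs, measuring dropouts does not exhaust power. The issue is bias and reliance on imputation, not sample size.

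**5. The exclusion rule.** At three calls a week, 6 sessions are 6/3 = 2 weeks. Anyone who stops for good by the end of week 10 of 12, and does not make sessions up, meets the exclusion in Section 5.4. Even if the gait speed were measured, that rule would keep it out of the main analyses, contrary to Sections 6.2.4 and 8.

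**The case against.** The strongest reply is that the plan takes missing outcomes seriously. Sections 6.2.4 and 8 direct the telephone data on dropouts into missing-at-random checks, joint modelling and multiple imputation. Section 9.1.1 reports that gait speed correlates with mobility complaints, so mobility information could be a useful auxiliary without being a trial outcome. A reader might infer that the effort spent on dropouts feeds no analysis; the text does not support that. What remains is that the model is unspecified, and that imputing a value is weaker than measuring one that was available.

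A reader might also infer that anyone who stops the calls loses the gait test. The documents do not say so. The schedule in Section 6.1 sets no session-count condition on the post visit, Section 5.4 plans a dose-response analysis by sessions attended, and ITT is to apply whether or not the intervention was received. The plan is silent on this participant, and silence is not exclusion. It is still a gap, because nothing tells staff to invite that person or when.

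Section 5.4 also has real retention measures: outside contacts, transport, a four-week visit window, and a $50 post-visit payment separate from the $25 for the calls. These help, but none is directed at people who have stopped.

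Three further limits stand. The 22% is not a prediction for this trial: it describes a completer analysis under one assumption, whereas the plan promises imputation. Some dropouts will refuse, move or be unreachable and stay missing whatever is done. Sections 3 and 9.1.2 refer to a registry list of outcomes that was not available, so the statement that mobility disability is not an outcome applies to these documents only.

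**Conclusion.** The point holds as a gap in outcome collection. For dropouts the plan gathers auxiliary information but makes no provision to measure the primary outcome, and for those who only stop the calls it neither bars nor secures the post visit. About 10 of 58 are expected to lack the outcome, on the plan's own enrolment and completion figures. Some of these could have been measured, and the ITT analysis would then rest on imputation where it need not.

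The direction and size of any bias are unknown. They depend on how dropouts differ between arms and on an imputation model that is not specified. The documents do not support saying that the result will be overstated by 22%, or that the dropout follow-up is useless. The change is worth making because it is cheap and protects the primary comparison.

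**What to change.** In Sections 5.4, 6.2.3, 6.2.4 and 8:

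1. Record stopping the phone sessions separately from withdrawing consent for further assessment.
2. Invite every randomised participant who has not withdrawn consent for assessment to the post visit, whatever number of sessions was completed. Time the visit from baseline, using the weeks 12–16 window in Section 6.1. The Précis (14–18 weeks after intervention) and Section 6.2.4 (12 months post-intervention) give other timings, and these passages must be reconciled.
3. Offer those who decline the full visit a reduced one with only the two walkway conditions, without MRI or the test battery.
4. Keep the telephone follow-up and adjudication as auxiliary information for those who remain unmeasured. Replacing them with the reduced visit would lose information on people who refuse any visit.
5. Reconcile the exclusion for 6 missed sessions in Section 5.4 with ITT in Sections 6.2.4 and 8, so that the gait speeds obtained are analysed.

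The change is mainly protocol wording. The running cost is staff time, transport and payment for the reduced visits. Transport and the $50 post-visit payment are already offered in Section 5.4, though the documents give no budget.

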9 STATISTICAL CONSIDERATIONS

9.1 General Design Issues

Our goal in this preliminary single-blind RCT is to determine the efficacy of motor imagery for improving gait and cognition in older adults. Baseline distribution of covariates will be compared to assess adequacy of randomization to produce comparable groups of participants using appropriate graphical procedures and summary statistics.

9.1.1. *Primary outcome*

Gait speed was recommended to FDA as the preferred outcome for RCTs (39) because of its good validity, reliability, sensitivity to change, and predictive validity for multiple adverse outcomes.(39) We have reported that gait speed highly correlates with mobility related activities in our community.(40)

Reliability: We have reported excellent test-retest reliability of gait speed on GAITRite (Kappa >0.9).(41) Gait speed correlates highly with complaints of mobility limitations, falls and dementia in our studies.(41, 42)

Practice effects: Gait speed improved only by <2% when tested twice 8 weeks apart in controls in our pilot study suggesting that longer intervals between gait assessments may help minimize practice effects.

Walking while talking test (WWT) is a novel ecologically valid mobility measure developed by our group.(43, 44) Our studies establish the incremental validity of WWT speed over NPW speed for predicting adverse outcomes such as falls, frailty and disability.(44) Other investigators have shown that training older adults on WWT like tasks translates into clinically relevant outcomes such as reduced falls, better balance, or improved function.(45) Hence, establishing the efficacy of motor imagery on our co-primary outcome of WWT speed alone could be of high clinical impact and relevance (irrespective of its effect on NPW speed).

Reliability: We reported good inter-rater reliability ($r = 0.602$) on a previous WWT version.(43) In 31 EAS subjects, we had excellent test-retest ($r = 0.935$) and inter-rater reliability ($r = 0.918$) for WWT speed.

9.1.2. Secondary and Tertiary outcomes.

Cognitive performance during the WWT – number of correct letters generated during WWT will be the main cognitive outcome. Additional cognitive/executive function tasks, including the WAIS-III Letter Number Sequencing Test (46), Stroop Color and Word Test (47), Trail Making Test (48) and Flanker Interference Task (49) will also be administered to determine if there are any far-transfer effects of our imagined gait intervention, and to carefully identify appropriate outcome measures for upcoming studies. Improved performance on the Stroop test following motor imagery training has been shown in individuals with Parkinson's disease (13), and we have previously shown improved performance on the Letter Number Sequencing Task in cognitively-healthy older adults following a cognitive intervention (50). Additional neuropsychological measures of processing speed, language, and memory will also be examined (see ee Clinicaltrials.gov-NCT02762604 for a comprehensive list).

Change in blood-oxygen-level-dependent (BOLD) signal will be examined during single (imagined walking) and dual task (imagined walking-while-talking) walking conditions. Changes in BOLD signal has been shown following physical and cognitive interventions in the past (51-53).

Additional variables/potential covariates will be recorded and carefully examined for potential inclusion as covariates or outcome measures in upcoming full-scale RCT, including stride length (cm), double support time (s), cadence (steps/min), swing time (s), stance time, stride length variability (SD), swing time variability (SD), the Geriatric Depression Scale (54), Medical Illnesses and Medication questionnaires (26, 55), Cognitive and Physical leisure activity questionnaire (56-58), Falls (59), Obesity (assessed with weight, waist circumference, and BMI (kg/m^2)), Vision (Snellen's chart), Disability (7 ADLs using the scale developed by Gill and colleagues (60, 61), IADL (62, 63), Blood pressure (Sitting/Standing), Gray Matter Volume/Atrophy (T1-Weighted structural images) White Matter Integrity (Diffusion Tensor Imaging; DTI) and White Matter Hyper intensities (Fluid-Attenuated Inversion Recovery; FLAIR).

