Study Title

Motor Imagery: A Pilot Intervention for Improving Gait and Cognition in the Elderly

Objectives:

Primary. Compared to a visual imagery intervention group, participants who are enrolled in the motor imagery intervention (MI) group will demonstrate:

P1: Significant improvements in gait speed during actual Walking and Walking While Talking

Secondary. Compared to a visual imagery intervention group, participants who are enrolled in the motor imagery intervention (MI) group will show:

P 2.1: Significant improvements in cognitive performance during Talking and Walking While Talking

P 2.2: Change in blood-oxygen-level dependent signal during Walking and Walking While Talking

Design and Outcomes

The investigators propose to conduct a single-blind randomized clinical trial to test the efficacy of a phone-based motor imagery intervention for improving gait and cognition in older adults between 65 and 85 years old

[figure not shown]

Figure 1. Participant Flow

Interventions and Duration

Participants will be randomized into either a 12-week phone-based motor imagery intervention or visual imagery intervention (active control condition). Both groups will complete 36 (15-minute) sessions (9 hours).

Participants will receive gait, mobility, cognitive and neuroimaging assessments at baseline and post-intervention (14-18 weeks after intervention). Baseline and post-intervention assessments will last about 3 hours over 1 day.

Sample Size and Population

We will enroll 48 cognitively-healthy older adults (24 in each group).

STUDY TEAM ROSTER

Principal Investigator:

[name]
Einstein College of Medicine,
[name]
[contact]
[contact]

[contact]

Main responsibilities/Key roles: She will coordinate efforts between team members, supervise implementation of study measures and supervise data collection. She will develop data analysis plans as well as scientific presentations and manuscripts based on the research findings.

Mentor:

[name]
Albert Einstein College of Medicine,
[name]
[contact]
[contact]

[contact]

Main responsibilities/Key roles: He will be responsible for the oversight of [name] responsibilities and for establishing benchmarks to ensure successful completion of this intervention. He will also be involved in developing data analysis plans as well as scientific presentations and manuscripts based on the research findings.

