The first aim of this research is to establish the efficacy of this imagined gait protocol to improve gait and EF in the elderly. We propose a pilot Randomized Clinical Trial (RCT) of 48 cognitively-healthy elderly adults who will be randomly assigned to an imagined gait intervention or an Active Control (AC; non-mobility related visual imagery) condition. The imagined gait (or AC) protocol will be administered during each study visit, and over the phone three times a week for three months (15 min/session, total of 36 sessions). Each participant will complete two study visits (pre and post). Pre-post intervention changes in gait velocity (cm/s) and cognitive performance (percent of correct letters provided; (correct/error x correct) x 100) during actual W, T and WWT will be our primary outcome measures. Age, Sex and Education will be covariates in all analyses. Other variables/covariates will be recorded (e.g. medical illnesses and history of falls), and carefully examined for potential inclusion as covariates in upcoming full-scale RCT.

The second aim is to determine neuroplasticity changes in response to our imagined gait intervention. To this end, participants will complete the imagined gait protocol (iW, iT and iWWT) during fMRI scanning at the pre and post-intervention study visits. We predict that our imagined gait protocol engages neural systems linked to actual gait and EF, while the AC condition engages neural systems linked to visual processing and imagery in general. We further predict that the neural systems engaged during our imagined gait protocol are strengthened following our imagined gait intervention.

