5 STUDY INTERVENTIONS

5.1 Interventions, Administration, and Duration

During **gait imagery training**, participants will be trained to iW, imagine talking (iT: reciting alternate letters of the alphabet out loud) and iWWT. They will be instructed to close their eyes during imagery, use both visual and kinesthetic imagery, and pay equal attention to both tasks in the iWWT condition. Seated at a desk, they will then complete two trials of imagery training in 16-seconds blocks for approximately 15 minutes. Imagery instructions will be presented auditorily, and the beginning and the end of a block will be initiated with a tone. During the first trial,

instructions will be detailed (i.e. “Imagine Walking: At the start of the next tone, close your eyes and imagine or envision yourself walking on the mat. At the start of the following tone, stop, and wait for further instructions”), but during the second trial they will simply be prompted to begin at the start of the tone (e.g. “Imagine Walking”). Following each trial, participants will be asked to evaluate the quality of their visual and kinesthetic images on a scale from 1 (no image; no sensation) to 5 (image as clear as seeing; as intense as executing the action). During **visual imagery training**, participants will be trained to imagine a set of concrete objects (e.g. giraffe) from a standardized set of pictures (36) that have been normed for name agreement, image agreement and visual complexity. Again, they will be instructed to close their eyes during imagery and will complete two trials of imagery training in 16 second blocks for approximately 15 minutes. Imagery instructions will be presented auditorily and the beginning and the end of a block will be initiated with a tone. Following each trial participants will be asked to evaluate the quality of their visual and kinesthetic images on a validated scale from 1 to 5 (37, 38).

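### The main cognitive outcome is an unscaled count of letters spoken during WWT; if WWT trials end by distance, which the protocol does not state, the count is tied to co-primary WWT speed

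*Combined protocol and SAP*

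**What the plan says.** Section 3 states the primary outcome: "The primary outcome is post-intervention change in gait speed during actual walking and walking while talking". Section 1.1 gives the measure as "gait speed (cm/s) during actual Walking and Walking While Talking using an instrumented walkway", and section 9.1.1 treats WWT speed as a co-primary outcome that could matter on its own.

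The secondary hypothesis in the Précis and section 1.2 is "Significant improvements in cognitive performance during Talking and Walking While Talking". Two places say how the letters are scored:

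- Section 9.1.2: "number of correct letters generated during WWT will be the main cognitive outcome".
- Section 2.1, Study Rationale (first aim): "percent of correct letters provided; (correct/error x correct) x 100". The same sentence says that gait velocity and this score "during actual W, T and WWT will be our primary outcome measures", although sections 1.2, 3 and 9.1.2 place cognitive performance among the secondary outcomes.

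Section 5.1 describes the talking task as "reciting alternate letters of the alphabet out loud". Covariates are age, sex and education (section 9.4). Section 9.4.2 names models for the Trail Making, Letter Number Sequencing, Stroop and Flanker tests, but none for the letter score.

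**The concern.** How many letters a person recites depends on how long they have to recite them. If a WWT trial is one or more passes over a set distance, the participant's own walking speed sets that time. The intervention is meant to raise this speed. A gain on the co-primary outcome would then reduce the time available for the main cognitive outcome, and nothing in the plan adjusts for it: there is no rate, and neither walking time nor speed is a covariate.

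Two misreadings could follow. A real gait benefit with no change in talking could appear as a cognitive cost, and a participant who slows down to concentrate could appear cognitively improved. Section 9.1.2 also looks to this trial to identify outcome measures for later studies, so a confounded score could be carried forward.

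**Working it through.** **The plan's own figure.** The only behavioural sample size is n = 34, for gait speed (section 9.2: alpha 0.05, power 0.80, f = 0.25). With 2 groups, m = 2 repeated measurements and an assumed correlation of 0.5 (not stated), the noncentrality is f² × N × m/(1 - 0.5) = 0.0625 × 34 × 2/0.5 = 8.5. Power is 0.807 at N = 34 and 0.781 at N = 32, so 34 reproduces. No sample size is given for the letter score, and nothing below changes the 34.

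**What sets the length of an actual WWT trial.**

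- Walkway length: not stated.
- Number of passes: not stated.
- End-of-trial rule (distance or time): not stated.
- Duration of actual Talking: not stated.
- Only task duration given: 16-second blocks, for imagery (section 5.1).

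The instrumented walkway, and the imagery script's mention of a mat (section 5.1), make a distance rule likely but do not establish it.

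**Case A: the trial ends by distance.** Talking time = distance/speed, so count = letter rate × distance/speed. With speed raised by a proportion g and the letter rate unchanged, the count is multiplied by 1/(1+g). Distance cancels, so the percentage does not depend on walkway length.

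| Assumed speed change | Count multiplier | Change in count | Change in letters per second |
|---|---|---|---|
| +2% | 1/1.02 = 0.980 | -2.0% | 0% |
| +5% | 1/1.05 = 0.952 | -4.8% | 0% |
| +10% | 1/1.10 = 0.909 | -9.1% | 0% |
| +15% | 1/1.15 = 0.870 | -13.0% | 0% |
| +20% | 1/1.20 = 0.833 | -16.7% | 0% |
| -10% (slowing) | 1/0.90 = 1.111 | +11.1% | 0% |

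The letter rate must itself rise by g for the count to stay level. For scale, with assumed values of 610 cm, 60 cm/s and 1 letter per second, a trial lasts 610/60 = 10.2 s and gives 10.2 letters. At 66 cm/s it lasts 9.2 s and gives 9.2 letters.

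**Case B: the trial runs for a fixed time.** Speed does not enter, and the bias is zero. Count and letters per second then differ only by a constant, so they give the same comparison.

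**The score in section 2.1.** A true percentage, correct/(correct + errors), does not change with trial time: 8 correct and 1 error give 8/9 = 88.9%, and shortening the trial scales both terms equally. The printed formula is something else. Read left to right, 8 correct and 1 error give 8/1 × 8 × 100 = 6400. With the product as denominator, the result is 8/(1 × 8) × 100 = 100 despite the error. Both readings are undefined at zero errors.

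**The case against.** The strongest reply is that the coupling rests on a fact the documents do not contain. No section says that WWT ends by distance. Section 10.3.4 mentions a MOP, which is not part of these documents and could hold the trial rules. This stands, so the point has to be conditional.

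Second, section 2.1 offers a percentage. If that became the outcome and were computed correctly, the coupling would disappear. A reader might infer that the problem remains whichever letter score is adopted; it does not. But section 9.1.2, the section that defines outcomes, names the count as main, and the formula in 2.1 is unusable as printed. A correct percentage would also measure accuracy without output: three letters, all correct, scores 100%.

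Third, the trial predicts better cognitive performance. If the letter rate rises by more than speed, the count still rises. A reader might infer that success on gait must lower the cognitive outcome. The arithmetic supports only a downward bias, which becomes a fall when the letter rate rises by less than speed.

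Fourth, the size is not anchored to this trial. The only percentage change in gait speed in the documents is under 2%, in controls retested at 8 weeks (section 9.1.1), and that is not a treatment effect. No SD for the letter count is given, so the bias cannot be set against its noise. This also stands.

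Fifth, one might infer that gait and cognition could no longer be read together, or that a Talking-versus-WWT contrast would produce a spurious three-way interaction. A rate can be derived later if trial times are kept, though it would not be the prespecified outcome. Section 9.4.2 specifies no such contrast for letters.

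**Conclusion.** The concern holds in conditional form. Two things are certain from the text: the letter outcome has two incompatible definitions, one with a formula that is not a percentage, and the count named as main has no time denominator and no stated trial-ending rule. If WWT ends by distance and the letter rate is unchanged, the count is biased against the faster arm by 1 - 1/(1+g): 2.0%, 4.8% or 9.1% for assumed speed gains of 2%, 5% or 10%. If WWT runs for a fixed time, the bias is zero. Whether it would be material against the spread of letter counts cannot be judged from the documents. The outcome is secondary in a pilot, so the consequence is a cognitive result that may be hard to interpret. The primary analysis is not at risk. The change is still worth making: a rate removes the coupling under a distance rule and loses nothing under a time rule.

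**What to change.** 1. In section 9.1.2, define the main cognitive outcome as correct letters per second of trial time. Take WWT time from the walkway record and note the duration of each Talking trial. Letters and time must cover the same interval.
2. Report accuracy beside it as correct/(correct + errors).
3. Put the same definition in section 2.1 in place of the printed formula, and align that sentence with the secondary status given in sections 1.2, 3 and 9.1.2.
4. State how actual WWT and Talking trials end: by distance (length and number of passes) or by time.

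The cost is a few sentences of text and a recorded duration for each Talking trial. Walking time should follow from the walkway measurement. No visit, test or sample-size figure changes.
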